1.3.2. Schedule of Activities for Maternal Participants Who Were Originally Assigned to Placebo

Visit Number (Maternal Participants)	101	102	103
Visit Description	1-Month Postdelivery Follow-up Vaccination 3	Vaccination 4	1-Month Telephone Contact Follow-up
Visit Window (Days)	21 to 35 Days After Delivery	19 to 23 Days After Visit 101	28 to 35 Days After Visit 102
Type of Visit	Clinic	Clinic	Phone Call
Confirm the participant originally received only placebo at Vaccination 1/2. Secondary confirmation by another site staff member is required	X		
Collect prohibited medication use	X	X	X
For participants who are HIV-positive, record latest CD4 count and HIV viral load			X
Review and consider eligibility	X	X	
Review temporary delay criteria	X	X	
Collect blood sample for immunogenicity assessment	~20 mL		
Obtain nasal (midturbinate) swab	X	X	
Obtain vaccine vial allocation via IRT	X	X	
Administer BNT162b2	X	X	
Assess acute reactions for at least 30 minutes after study intervention administration	X	X	
Collect AEs and SAEs as appropriate	X	X	X
Contact the participant by telephone			X

1.3.3. Schedule of Activities for Infant Participants

Visit Number (Infant Participants)	1	2	3	Unplanned	Unplanned
Visit Description	Delivery	1-Week Postdelivery Follow-up	6-Months-of-Age Follow-up	Potential COVID-19 Illness Visit	Potential COVID-19 Convalescent Visit
Visit Window (Days)	Varies	7 to 10 Days After Delivery	160 to 200 Days After Delivery	Optimally Within 3 Days After Potential COVID-19 Illness Onset	28 to 35 Days After Potential COVID-19 Illness Visit
Type of Visit	Hospital	Phone Call	Clinic		
Assign single participant identifier	X				
Record demography and available birth information	X				
Measure vital signs	X				
Perform physical examination	X				
Record concomitant medication associated with an adverse event/serious adverse event	X	X	X		
Review eligibility	X				
Review continued eligibility		X	X		
Record breastfeeding information		X	X		
Collect blood sample for immunogenicity assessment (up to ~5 mL per blood sample depending on weight)			X		X
Cord blood sample (~10 mL) for immunogenicity assessment	X ^a				
Record adverse events	X	X ^b	X ^b	X	X
Record serious adverse events and adverse events of special interest	X	X	X	X	X
Collect prohibited medication use				X	X
Obtain nasal swab				X	
Collection of COVID-19-related clinical and laboratory information (including local diagnosis)				X	X
Collect e-diary or assist the maternal participant to delete application			X		

Abbreviations: HIV = human immunodeficiency virus; IRT = interactive response technology.

- a. If cord blood is unavailable, a blood sample may be collected from the infant participant up to 72 hours after birth but preferably within 24 hours after birth.
- b. Active AE collection through 1 month of age.

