To describe the immune response over time and persistence of prophylactic BNT162b2 when administered to maternal participants 18 years of age or older vaccinated at 24 to 34 weeks' gestation.	In maternal participants complying with the key protocol criteria (evaluable maternal participants) from each vaccine group: 
 • GMCs/GMTs, at baseline (before Dose 1), 2 weeks after Dose 2, 1 month after Dose 2, at delivery, and 6 months after delivery • GMFRs from baseline through 2 weeks after Dose 2, 1 month after Dose 2, at delivery, and 6 months after delivery 	
 • Full-length S-binding IgG levels • SARS-CoV-2 neutralizing titers
To assess the safety of maternal immunization in infants born to maternal participants 18 years of age or older who were vaccinated with BNT162b2 during pregnancy.	In infants born to maternal participants receiving at least 1 dose of study intervention from each vaccine group, the percentage of infants with: 
 • Specific birth outcomes • AEs from birth through 1 month of age • SAEs and AESIs (major congenital anomalies, developmental delay) through 6 months of age 	
 • Specific birth outcomes • AEs from birth through 1 month of age • SAEs and AESIs (major congenital anomalies, developmental delay) through 6 months of age
To describe the immune response in infants born to maternal participants vaccinated with prophylactic BNT162b2 during pregnancy.	In infants born to evaluable maternal participants from each vaccine group: 
 • GMCs and GMFRs, at birth and 6 months after delivery 	
 • Full-length S-binding IgG levels

Objectives^a	Estimands	Endpoints
Exploratory	Exploratory	Exploratory
To describe the incidence of confirmed COVID-19 among maternal participants who were vaccinated with BNT162b2.	In maternal participants who received BNT162b2 at initial randomization: 
 Incidence per 1000 person-years of follow-up 	
 COVID-19 incidence per 1000 person-years of follow-up based on central laboratory or locally confirmed NAAT

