8.3.1. Time Period and Frequency for Collecting AE and SAE Information

The time period for actively eliciting and collecting AEs and SAEs (“active collection period”) for each maternal participant including her fetus begins from the time the maternal participant provides informed consent, which is obtained before participation in the study (ie, before undergoing any study-related procedure and/or receiving study intervention), through and including a minimum of 28 calendar days after the last administration of the study intervention.

In this study, the investigator and site staff will ensure the active elicitation and collection of AEs and SAEs through Visit 4.

From Visit 4 through Visit 8, SAEs will be collected for maternal participants originally randomized to BNT162b2. In addition, AEs occurring up to 48 hours after blood draws and collection of nasal swabs that are related to study procedures must be reported in the CRF.

Additionally, for those maternal participants who originally received placebo but go on to receive BNT162b2 at Visit 101 and Visit 102, AEs and SAEs will be collected through and 1 month after the second dose of BNT162b2 (Visit 103).

For the infant participant, the time period for actively eliciting and collecting nonserious AEs (“active collection period”) begins at birth and continues through and including 1 month after birth. SAEs and AESIs will be collected from birth through and including 6 months of age.

Follow-up by the investigator continues throughout and after the active collection period and until the AE or SAE or its sequelae resolve or stabilize at a level acceptable to the investigator and Pfizer concurs with that assessment.

For maternal participants who are screen failures, the active collection period ends when screen failure status is determined.

If the participant withdraws from the study and also withdraws consent for the collection of future information, the active collection period ends when consent is withdrawn.

If a participant definitively discontinues or temporarily discontinues study intervention because of an AE or SAE, the AE or SAE must be recorded on the CRF and the SAE reported using the Vaccine SAE Reporting Form.

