8.11.1.5. Visit 6 – 1-Week Postdelivery Follow-up (Telephone Call: 7-10 Days After Delivery)

- Record nonstudy vaccinations as described in [Section 6.5](#).
- Collect and record concomitant medication associated with AE/SAEs.
- Ensure and document that the participant is still eligible for continued participation.
- If not obtained at the time of delivery, update pregnancy outcome information, including vital status of the infant (live, stillbirth, etc), mode of delivery (vaginal delivery or cesarean delivery), and the use of any assisted devices (forceps or vacuum).
- Record AEs and SAEs as described in [Section 8.3](#).

- If Visit 6 occurs within 1 month after study vaccination: Ask the participant to contact the site staff or investigator if the participant experiences acute chest pain, shortness of breath, or palpitations (see [Section 8.14](#)).
- Ask the participant to contact the site staff or investigator (this could be via the COVID-19 illness e-diary) immediately if she experiences any COVID-19 illness symptoms as detailed in [Section 8.13](#).
- Schedule an appointment for the participant to return for the next study visit.
- Complete the source documents.
- The investigator or an authorized designee completes the CRFs.

8.11.1.6. Visit 7 – 1-Month Postdelivery Follow-up (Clinic: 21 to 35 Days After Delivery)

- All participants will be unblinded. Maternal participants who received BNT162b2 will follow the procedures below and those who received placebo will follow the procedures in [Section 8.17](#).
- Phase 3 only: For participants who are HIV-infected, record HIV viral load and CD4 count results from the most recent test performed since their last visit (if any).
- Record nonstudy vaccinations as described in [Section 6.5](#).
- Collect and record concomitant medication associated with AE/SAEs.
- Ensure and document that the participant is still eligible for continued participation.
- Record AEs and SAEs as described in [Section 8.3](#).
- Ask the participant to contact the site staff or investigator (this could be via the COVID-19 illness e-diary) immediately if she experiences any COVID-19 illness symptoms as detailed in [Section 8.13](#).
- Schedule an appointment for the participant to return for the next study visit.
- Complete the source documents.
- The investigator or an authorized designee completes the CRFs.

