- Ask the maternal participant to contact the site staff or investigator (this could be via the COVID-19 illness e-diary) immediately if the infant participant experiences any COVID-19 illness symptoms as detailed in [Section 8.19](#).
- Complete the source documents.
- The investigator or an authorized designee completes the CRFs.

8.18.2. Visit 2 – 1-Week Postdelivery Follow-up (Telephone Call: 7-10 Days After Visit 1)

- Ensure and document that the infant is still eligible.
- Record breastfeeding information.
- Collect and record concomitant medication associated with AE/SAEs.
- Record AEs, SAEs, and AESIs as described in [Section 8.3](#).
- Schedule an appointment for the participant to return for the next study visit.
- Ask the maternal participant to contact the site staff or investigator (this could be via the COVID-19 illness e-diary) immediately if the infant participant experiences any COVID-19 illness symptoms as detailed in [Section 8.19](#).
- Complete the source documents.
- The investigator or an authorized designee completes the CRFs.

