8.18.3. Visit 3 – 6-Months-of-Age Follow-up (Clinic: 160-200 Days After Visit 1)

- Record concomitant medication associated with SAEs.
- Record breastfeeding information.
- Collect a blood sample (approximately 5 mL) for immunogenicity testing. The volume of blood collected will be based on the weight of the infant (refer to [Table 1](#)).
- Record AEs, SAEs, and AESIs as described in [Section 8.3](#).
- Collect e-diary or assist the maternal participant to delete application.
- Complete the source documents.
- The investigator or an authorized designee completes the CRFs.

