6.2.3.2. Adverse Events

6.2.3.2.1. Main Analyses

- Estimand: The percentage of infant participants reporting AEs from birth through 1 month of age (Section 2.1).
- Analysis set: Safety population (infant) (Section 4).
- Analysis time point: Birth through 1 month of age.
- Analysis methodology: Descriptive statistics and 3-tiered approach (Section 5.2.1).
- Intercurrent events and missing data: Missing data will not be imputed except for partial AE start dates (Section 5.3).
- Reporting results: Counts, percentages, and the associated Clopper-Pearson 95% CIs for infant participants with AEs from birth through 1 month of age will be provided for each vaccine group (according to the study intervention the maternal participants received). For both Tier 1 (if any) and Tier 2 events, the between-group difference in proportions and the associated 95% CI based on the Miettinen and Nurminen² method will be provided. For Tier 1 events (if any), the asymptotic p-values for the difference in proportions will be provided. For Tier 3 events, counts and percentages will be provided for each vaccine group (according to the study intervention the maternal participants received).

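### No infant contact is scheduled at 1 month, so 64–77% of the nonserious infant AE window may rest on recall 4–6 months later by mothers who know their allocation

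*Protocol*

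**What the plan says.** Protocol Section 3 lists "AEs from birth through 1 month of age" among the secondary infant safety endpoints. SAP 6.2.3.2.1 turns this into an estimand, "The percentage of infant participants reporting AEs from birth through 1 month of age", reported by vaccine group. Between-group differences and Miettinen–Nurminen intervals are given for Tier 1 and Tier 2 events.

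Protocol 8.3.1 requires active elicitation of nonserious infant AEs and says the period "begins at birth and continues through and including 1 month after birth". SAEs and AESIs in infants run to 6 months of age.

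The infant schedule (Protocol 1.3.3, with 8.18.1 to 8.18.3) has three planned contacts: delivery, a telephone call "7 to 10 Days After Delivery", and a clinic visit at days 160–200. The AE row is marked at the last two with the footnote "Active AE collection through 1 month of age". There is no column for 1 month.

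The mother has a clinic visit at days 21–35. For BNT162b2 recipients it is Visit 7 (8.11.1.6), which opens with "All participants will be unblinded". Placebo recipients follow Visit 101 instead (8.17.1). Both list an AE step that points to Section 8.3. Neither mentions the infant.

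**The concern.** The plan commits to active elicitation through 1 month but schedules no infant contact at or near the end of that month. If sites follow the infant schedule as written, an event arising after the telephone call is next asked about at 6 months. By then every mother who attended the day 21–35 visit has been told her allocation.

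Two things are at stake. Nonserious newborn events are the kind that can be forgotten over several months, so the percentage could be too low in both arms. Reporting could also differ between arms, because the mother reporting the event and the staff recording it know what she received. The number of occasions on which a mother might mention an infant event also differs by arm after day 10. The SAP compares the arms on this endpoint without any caveat about how or when the events were ascertained.

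**Working it through.** The plan gives no figure on this point, so there is none to reproduce. The checks are arithmetic on the visit windows. The documents do not define 1 month in days, so 28, 30 and 31 days are all shown.

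**Share of the window after the call.** Share = (days in month − day of call) / days in month, with the call on day 7 or day 10 (Protocol 1.3.3).

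| Month | Call on day 7 | Call on day 10 |
|---|---|---|
| 28 days | 21/28 = 75% | 18/28 = 64% |
| 30 days | 23/30 = 77% | 20/30 = 67% |
| 31 days | 24/31 = 77% | 21/31 = 68% |

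So 18–24 days, or 64–77% of the window, come after the last early contact.

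**Recall lag to the day 160–200 visit.** For an event at the end of the month, the lag is 160 − 31 = 129 to 200 − 28 = 172 days. For an event just after the call, it is 160 − 10 = 150 to 200 − 7 = 193 days. Overall this is about 4 to 6 months.

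**Scheduled maternal contacts between days 10 and 160, by arm** (Protocol 1.3.1 and 1.3.2):
- BNT162b2: Visit 7 at days 21–35, then nothing until Visit 8 at days 160–200. One contact.
- Placebo: Visit 101 at days 21–35; Visit 102 at 21 + 19 = 40 to 35 + 23 = 58 days; Visit 103 at 40 + 28 = 68 to 58 + 35 = 93 days. Three contacts.

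The maternal questioning also differs in kind. Under Protocol 8.3.1 the placebo arm is in active AE and SAE collection to Visit 103. From Visit 4, the BNT162b2 arm is in SAE collection, plus procedure-related AEs within 48 hours.

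**How few events matter.** SAP 5.2.1 makes a preferred term Tier 2 when at least 1% of one group report it. With about 175 per group (Protocol 9.2) and singleton pregnancies, 0.01 × 175 = 1.75, so two infants are enough. One or two lost or differentially recalled events can decide whether a term gets a between-group interval.

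**What an added step at the day 21–35 visit would leave uncovered.** At a day-21 visit: 7/28 = 25%, 9/30 = 30% or 10/31 = 32%. At a visit on or after the last day of the month: 0%.

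**How many infants that step could still reach.** Enrollment ended on 25 Oct 2021 (Protocol 4.1), and amendment 5 is dated 08 Mar 2022 (SAP Section 1), which is 134 days later. Assume the last woman was vaccinated on the closing date at 24 weeks, the earliest permitted. Delivery at 40 weeks is then 112 days on, and her infant is 134 − 112 = 22 days old at the amendment. With delivery at 42 weeks the infant is 134 − 126 = 8 days old. The 40–42 week range is an assumption. A first dose given after the closing date would make the infant younger still. Women enrolled earlier or at a later gestation had delivered sooner, so nearly all infants were past the visit.

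**The case against.** The strongest reply is that late recall is not prescribed. Section 8.3 states that its procedures cover infant as well as maternal participants and that parents are questioned about AEs. The AE step at Visits 7 and 101 points to that section. A site could therefore ask about the infant at days 21–35 and collect most of the window then. The maternal schedule's footnote limiting AE recording at Visit 7 to 48 hours after a draw or swab does not speak to infant AEs. This stands: a reader might infer that every event from about day 11 onward is first asked about at 6 months, and the documents do not support that. They leave open whether anyone asks earlier.

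Other parts of the reply also stand.

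- Unplanned infant COVID-19 illness and convalescent visits record AEs, and mothers may report spontaneously. These routes depend on symptoms or initiative and do not replace elicitation, but it is *scheduled* contact that is missing.
- Anything reported before the day 21–35 visit is reported blind. When that visit falls at or after the end of the month, the mother is blind throughout the window.
- A reader might infer from the order of the listed steps that AE questions follow unblinding. Visits 1, 2 and 102 say their steps are expected to be carried out stepwise; Visits 7 and 101 do not. The order is unspecified, not wrong.
- A reader might extend the point to the primary maternal SAE endpoint. SAEs are reported within 24 hours of awareness (8.3.1.1), so that endpoint does not hang on one question at the end of its window.
- The endpoint is secondary and descriptive, with no hypothesis test.

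The reply does not remove the gap. No section requires infant AE elicitation between the call and the 6-month visit, and nothing requires it to precede disclosure of allocation.

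**Conclusion.** The point holds as a gap between a stated requirement and the schedule meant to deliver it. Active elicitation is required through 1 month, but no infant contact is scheduled between days 7–10 and days 160–200, and the day 21–35 maternal visit does not expressly ask about the infant. As a result, 64–77% of the window *may* depend on recall about 4–6 months later by mothers who know their allocation. Three scheduled maternal contacts against one leave room for incidental infant reports to differ by arm.

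This rests on a month of 28–31 days and on sites doing no more than the schedule lists. The documents contain no data showing that under-reporting occurred, so its amount and direction by arm are unknown. Because infant SAEs and AESIs are collected to 6 months, the concern is mainly nonserious AEs. It limits how the infant AE comparison should be read and does not touch the primary endpoints.

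**What to change.** 1. In the infant schedule (Protocol 1.3.3) and in Sections 8.11.1.6 and 8.17.1, add infant AE elicitation to the existing day 21–35 maternal visit. Word it identically for both arms and require it to be completed before allocation is opened. A visit on day 21 would still leave 25–32% of the window to later contact, so this reduces the gap without always closing it. By amendment 5 it could reach few infants.

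2. For infants already past that visit, split the infant AE table in SAP 6.2.3.2 by onset date: on or before the Visit 2 call, and after it. Onset dates are already collected, and SAP 5.3 does not allow a wholly missing start date. The same section assigns partial dates to the earliest possible day, which could move a late-recalled event into the early column. Events with a partial onset date that could fall on either side should be shown separately.

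3. If the date of first report is captured, which the documents do not show, also split by report before or after the mother's unblinding date. Present only events reported before unblinding as the blinded comparison. Without report dates, use onset up to Visit 2 as the proxy, noting that an early-onset event may still have been reported late. Caveat the remainder as subject to late, unblinded recall.

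The cost is one line at a visit already held, one table split and a sentence of interpretation. The price is smaller counts per cell.

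### Infant nonserious AEs are analysed from birth to 1 month, but no infant contact is scheduled between the day 7-10 call and the day 160-200 visit, so much of the window may be collected late and after unblinding

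*Protocol*

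**What the plan says.** Three places set the window. Protocol Section 8.3.1 says the active collection period for infant nonserious AEs "begins at birth and continues through and including 1 month after birth". Footnote b of the infant schedule (Protocol 1.3.3) reads "Active AE collection through 1 month of age" and is attached to the AE row at infant Visits 2 and 3. SAP 6.2.3.2.1 defines the estimand as "The percentage of infant participants reporting AEs from birth through 1 month of age" and repeats the window under "Analysis time point: Birth through 1 month of age". It adds Miettinen-Nurminen intervals for the between-group difference in Tier 2 events.

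The scheduled infant contacts are delivery, a telephone call "7 to 10 Days After Delivery", and "6-Months-of-Age Follow-up (Clinic: 160-200 Days After Visit 1"). Sections 8.18.1 to 8.18.3 agree with the schedule.

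The mother has a clinic visit 21 to 35 days after delivery: Visit 7, or Visit 101 if she originally received placebo. The first instruction under Visit 7 (Section 8.11.1.6) is "All participants will be unblinded". Later items record AEs and SAEs by pointing to Section 8.3. In the maternal schedule (1.3.1), AE recording at Visit 7 carries footnote d, which confines it to AEs within 48 hours of a blood draw or swab. The Visit 101 text (8.17.1) also points to Section 8.3, and its schedule (1.3.2) has no 48-hour limit. Neither procedure list names the infant in connection with AEs.

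**The concern.** A reader of the results would take a birth-to-1-month percentage to mean that mothers were asked about the whole month at about the time it happened. The schedule secures that only up to the day 7-10 call. For the rest of the month, the next scheduled infant contact is about five to six months later. By then every mother who completed Visit 7 or 101 knows her allocation, and under Protocol 6.3.2 and 6.3.3 so do the site staff who question her.

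Infant AEs through 1 month are part of a secondary safety objective, in a study designated a post-authorization safety study. If capture after the call is incomplete, the percentages change. If it differs by arm, so does the between-group difference.

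**Working it through.** The plan states no coverage figure, so there is none to reproduce. The check is arithmetic on the visit windows.

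**Inputs.** Call on day c = 7 or 10 and Visit 3 on day 160 to 200 (Protocol 1.3.3). Maternal visit on day 21 to 35 (1.3.1, 1.3.2). The documents do not give 1 month in days, so I take M = 28, 30 or 31.

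**1. Share of the window after the last scheduled infant contact, (M − c)/M.**

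| M | call on day 10 | call on day 7 |
|---|---|---|
| 28 | 18/28 = 64.3% | 21/28 = 75.0% |
| 30 | 20/30 = 66.7% | 23/30 = 76.7% |
| 31 | 21/31 = 67.7% | 24/31 = 77.4% |

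**2. Lag to Visit 3.** The shortest is an event on day 31 with Visit 3 on day 160: 160 − 31 = 129 days. The longest is an event straight after a day-7 call with Visit 3 on day 200: 200 − 7 = 193 days.

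**3. Does the maternal visit close the gap?** It falls at or near the end of the month, so it could. Three things stand against relying on it:
- The infant is not named in the AE instruction.
- At Visit 7 disclosure is listed first, and Visit 101 begins by confirming that the mother received placebo.
- Footnote d, read literally, leaves little to record at Visit 7, because the maternal schedule marks no blood draw or swab there.

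**4. Contacts by arm after unblinding.** Placebo mothers have Visit 101 (day 21-35), Visit 102 (19-23 days later) and Visit 103 (28-35 days after that). Visit 103 falls between day 21 + 19 + 28 = 68 and day 35 + 23 + 35 = 93. AEs and SAEs are collected at all three. BNT162b2 mothers have Visit 7 and then no scheduled contact until day 160-200. An infant AE mentioned in passing has more chances of being recorded in the placebo arm.

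**5. How few reports matter.** A preferred term enters Tier 2 at 1% in either group. With 175 mothers per group (Protocol Table 5), assuming one infant each and no losses, 0.01 × 175 = 1.75, so two infants suffice.

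**6. Effect of asking at Visit 7/101.** The share left to a later contact becomes max(0, M − v)/M for a visit on day v. It is 0% when the visit falls on or after the last day of the month. For a day-21 visit it is 7/28 = 25%, 9/30 = 30% or 10/31 = 32%. The uncovered share falls from 64-77% to 0-32%.

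**The case against.** The strongest reply is that the protocol already creates the duty. Section 8.3 says its procedures apply to infants as well as mothers and that parents will be questioned about AEs. Section 8.3.1 sets the infant period at 1 month, and Visits 7 and 101 point to that section. Silence about the infant makes the visit lists ambiguous. It does not show that nobody asks.

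There are other routes too. Spontaneously reported AEs go on the CRF (8.3.1.2). Under Section 8.19 the mother must contact the site for infant fever, cough, shortness of breath, diarrhea, vomiting or a COVID-19 diagnosis, and AEs are recorded at the illness and convalescent visits that follow. Every endpoint is descriptive.

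Most of this stands, and it rules out a stronger reading: that every infant AE after the call is first asked about at 6 months, from recall. The documents do not say so. They leave open that a site asks at Visit 7 or 101, and they provide for event-driven reports. A reader might also infer that the percentage must be too low, or that a spurious difference of some size would follow. The documents give no capture rates, by arm or overall, so neither can be claimed.

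What the reply does not supply is a scheduled, expressly required infant elicitation between day 10 and day 160. Spontaneous and symptom-triggered reports do not replace general AE questioning, and a site following Visit 7 in the listed order would hear of infant AEs only after disclosure.

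**Conclusion.** The gap is real and should be corrected. Active elicitation is promised for the whole month, but scheduled infant contact covers only the first 7-10 days of it. About 64-77% of the window may be collected with a lag of about 129-193 days and after unblinding, apart from spontaneous reports and illness visits. After unblinding, opportunities for incidental capture also differ by arm.

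The percentages rest on a month of 28 to 31 days and on the stated visit windows. They measure time without a scheduled infant contact, not events missed. The size and direction of any bias are unknown. The point concerns nonserious AEs mainly. SAEs and AESIs share the same schedule, but their collection runs through 6 months, so they are less affected.

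**What to change.** 1. In Protocol 1.3.3, 8.11.1.6, 8.17.1 and 8.18, state that infant AEs, SAEs and AESIs are elicited at the existing Visit 7 or 101 before allocation is disclosed, for any infant not yet past that visit. Say that footnote d of the maternal schedule does not restrict this.

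2. In SAP 6.2.3.2.1, keep the birth-to-1-month endpoint. Add a supplementary table, with between-group differences, of infant AEs by the contact at which they were reported and by whether that was before or after maternal unblinding. State post-unblinding collection as a limitation. Splitting by reporting contact is better than splitting by onset date, because a day-15 event reported promptly is not late recall.

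The cost is one CRF item and one extra table, with no new visit. The documents do not say whether the database identifies the contact at which an AE was reported. If it does not, a proxy such as the date of first entry would be needed.

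The first change reaches few infants. Enrollment ended on 25 October 2021. A woman vaccinated that day at 24 0/7 weeks reaches 40 weeks (assumed delivery) 16 × 7 = 112 days later, on 14 February 2022, so her Visit 7/101 falls on 7 to 21 March. Adding the 28-day screening allowance moves it to 4 to 18 April. SAP version 3 is dated 31 March 2022. For nearly all infants the supplementary table and the stated limitation are what remain available.
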